8.2.2. Protocol Deviations

Protocol deviations will be classified as "major" or "minor" on ongoing basis by the clinical study team and sponsor.

Major protocol deviations are defined as those deviations from the protocol likely to have an impact on the participant's rights, safety, well-being, and/or the validity of the data for analysis. Minor protocol deviations include all deviations from the protocol excluding the major protocol deviations.

Major protocol deviations and any action to be taken regarding the exclusion of participants or affected data from specific analyses are defined in the project-specific Protocol Deviation Assessment Plan.

The study team will identify the major protocol deviations related to efficacy or that may have impact on efficacy to determine the participants in the FAS to be excluded from the PPS prior to database lock in a blinded fashion. Some major protocol deviations may not lead to participants' data being excluded from the PPS.

The number and percentage of participants with a major protocol deviation in the FAS will be summarized by randomized treatment group. A by-participant listing of all protocol deviations will also be provided.

8.2.3. Demographics and Baseline Characteristics

This analysis will be based on the Safety Set and FAS.

Demographic data, such as age at randomization, sex, race, and ethnicity, years of education, employment history, current employment status, and baseline characteristics, such as height, weight, and body mass index (BMI) will be summarized using descriptive statistics by treatment group and overall.

Baseline characteristics related to the diagnosis and treatment of PD, cognitive performance and motor symptoms will also be summarized for:

- Years since initial diagnosis of PD (continuous)
- Diagnosis Criteria Level for PD-MCI (categorical: Level 1 [abbreviated], Level 2 [comprehensive])
- Medication for treating PD symptoms (categorical: No, Yes)
 - If yes, Clinical Status (categorical: On, Off)
 - *Note:* On is the typical functional state when patients are receiving medication and have a good, and Off is the typical functional state when patients have a poor response despite taking medications.
- WAIS-IV Coding test score (continuous)
[REDACTED]
[REDACTED]
[REDACTED]
[REDACTED]
[REDACTED]
[REDACTED]
- Total daily Levodopa Equivalent Dose (LED) at Screening (continuous)

Total daily LED at Screening will be calculated based on the conversion factor presented in [Appendix D](#).

By-participant listing of all demographics and baseline characteristics will also be provided by treatment group.

8.2.4. Medical History

This analysis will be based on the Safety Set.

Medical history collected at screening will be coded using the Medical Dictionary for Regulatory Activities (MedDRA), Version 22.0 or higher. Medical history data will be summarized by system organ class (SOC) and preferred term (PT).

Medical history will be listed by treatment group. Also, by-participant listing of Parkinson's disease history will be provided.

8.2.5. Prior and Concomitant Medications/Procedures

This analysis will be based on the Safety Set.

Medications and procedures will be recorded at each study visit during the study and will be coded using World Health Organization-Drug dictionary September 2015, or later and MedDRA Version 22.0 or higher, respectively.

All medications/procedures taken within 60 days prior to Screening through the duration of the study will be recorded, as well as all medications/procedures used to treat PD regardless of timing. Those medications/procedures taken and ended prior to the first dose of IP will be denoted "Prior". Those medications/procedures taken prior to the first dose of IP and continuing beyond the initiation of the IP or those medications/procedures started at the same time or after the initiation of the IP will be denoted "Concomitant".

Medications/procedures will be presented according to whether they are "Prior" or "Concomitant" as defined above. If medication/procedures dates are incomplete and it is not clear whether the medication/procedures are concomitant, it will be assumed to be concomitant.

Missing or partial dates will be imputed for medication/procedures. Algorithm for missing or partial start/end date is documented in [Appendix C](#).

Concomitant medications/procedures are further categorized as on-treatment and post-treatment as follows:

- On-treatment concomitant medications/procedures are those that have been used between first and last dose of IP (both inclusive) as well as medications started prior to first dose of IP and continue beyond the initiation of IP.
- Post-treatment medications/procedures are those that have been started after the last dose of IP.

Concomitant medications will be summarized on the Safety Set using Anatomical Therapeutic Chemical (ATC) level 1 and Standard Medication Name by actual treatment group. Concomitant procedures will be summarized on the Safety Set using SOC and PT by actual treatment group. By-participant listings of prior and concomitant (on-treatment and post-treatment) medications as well as procedures will also be provided.

8.2.6. Investigational Product Exposure

This analysis will be based on the Safety Set.

Total exposure duration to IP (in days), total drug exposure (in mg), and percent of planned exposure received (in %) will be summarized by actual treatment group.

Total exposure duration to IP (in days) is defined as the date of the last dose minus the date of first dose plus 1. Note that this does not exclude days when the dose has been missed.

Total drug exposure (in mg) is defined as the total IP in mg for SAGE-718 that was taken during the study. Total drug exposure for participants randomized to placebo is zero unless the participant has taken SAGE-718 by mistake, in which case the total exposure comes from SAGE-718 exposure. The dose taken will be considered as 0 mg on days the participant skips a dose.

Percent of the planned exposure received (in %) is defined as the total drug exposure, divided by planned exposure, times 100%.

- For participants randomized to SAGE-718 who complete the treatment period, the planned exposure is calculated as follows:
 - 40 days times 1.2 mg if Study Day of Day 42 Visit < 40
 - (Date of Day 42 visit – First Dose Date + 1) times 1.2 mg if Study Day of Day 42 Visit is 40 or 41
 - 42 days times 1.2 mg if Study Day of Day 42 Visit \geq 42
- For participants randomized to SAGE-718 who discontinue the treatment earlier than Day 42 Visit, the planned exposure is (Last Dose Date – First Dose Date + 1) times 1.2 mg for participants randomized to SAGE-718.
- For participants randomized to placebo, this measure is not applicable.

By-participant listing of IP administration and exposure will also be provided including participant ID, date of dose, planned exposure (mg), and actual exposure (mg).

8.2.7. Investigational Product Adherence

This analysis will be based on the FAS.

IP adherence (%) is defined as the number of capsules taken, divided by the number of capsules planned to be taken, times 100%. The planned number of capsules is defined as similar way as planned exposure.

- For participants who complete the treatment period, the planned number of capsules taken is defined as follows:
 - 40 if Study Day of Day 42 Visit < 40
 - (Date of Day 42 visit – First Dose Date + 1) if Study Day of Day 42 Visit is 40 or 41
 - 42 if Study Day of Day 42 Visit \geq 42
- For participants who discontinue the treatment earlier than Day 42 Visit, the planned exposure is (Last Dose Date – First Dose Date + 1).

Number and percentage of participants with IP adherence in categories (<80%, 80-100%, >100%) will be provided. By-participant listing of IP adherence will be provided.

8.3. Efficacy Analysis

The FAS and PPS will be used for all efficacy summary and analysis tables. Participants will be analyzed according to randomized treatment.

8.3.1. Definition of Efficacy Variables

8.3.1.1. Primary Efficacy Assessment

The WAIS-IV Coding test is a valid and sensitive measure of cognitive dysfunction impacted by many domains that correlates with real-world functional outcomes (e.g., the ability to accomplish everyday tasks) and recovery from functional disability. In-clinic administration of the WAIS-IV Coding test will use the traditional paper-and-pen format, in which the participant is required to identify the symbols matched to numbers using a key and write in the symbol beneath the associated number. The score is based on the total number of codes correctly completed over a 120 second time limit (higher scores reflecting better performance).

WAIS-IV Coding Test is collected at Baseline (Day -7), Day 1 (pre-dose), Day 14, Day 42 and Day 70.

[REDACTED]

A series of horizontal black bars of varying lengths, with a few small vertical black marks on the left side.

8.3.1.2.5. Penn Parkinson's Daily Activities Questionnaire-15 Knowledgeable Informant

Penn Parkinson's Daily Activities Questionnaire-15 Knowledgeable Informant (PDAQ-15 KI) is a caregiver-reported outcome that measures the cognitive IADL in PD. The instrument is completed by a KI to the patient. The PDAQ-15 KI was created as an abbreviated version of the PDAQ-50 consisting of 15 of the original 50 items and demonstrates strong psychometric properties across the spectrum of cognitive impairment. The items are scored for difficulty in performing each IADL on a "none" (4), "a little" (3), "somewhat" (2), "a lot" (1) and "cannot do" (0) with the total score ranging from 0 to 60 (higher scores indicating better IADL function). PDAQ-15 KI is collected on Baseline (Day -7), Day 42 and Day 70.

The key outcome measure is a total score. Other outcome measures are each individual items.

A series of horizontal black bars of varying lengths, likely representing redacted text or sensitive information.

A horizontal bar chart consisting of 20 bars. The bars are black and of varying lengths, representing data points. The lengths of the bars are approximately: 15, 18, 10, 12, 14, 16, 18, 10, 12, 14, 16, 18, 10, 12, 14, 16, 18, 10, 12, 14. The bars are positioned in a grid-like pattern, with some bars having small gaps between them.

A horizontal bar chart showing the distribution of 1000 samples across 20 categories. The x-axis represents the number of samples (0 to 1000), and the y-axis represents the category index (0 to 19). Categories 0, 1, 2, 3, 5, 6, 7, 8, 9, 11, 12, 13, 14, 15, 16, 17, 18, 19, and 20 have zero samples. Categories 4, 10, and 19 have 1 sample each. Categories 10, 11, 12, 13, 14, 15, 16, 17, 18, and 19 have 2 samples each. Categories 10, 11, 12, 13, 14, 15, 16, 17, 18, and 19 have 3 samples each. Categories 10, 11, 12, 13, 14, 15, 16, 17, 18, and 19 have 4 samples each. Categories 10, 11, 12, 13, 14, 15, 16, 17, 18, and 19 have 5 samples each. Categories 10, 11, 12, 13, 14, 15, 16, 17, 18, and 19 have 6 samples each. Categories 10, 11, 12, 13, 14, 15, 16, 17, 18, and 19 have 7 samples each. Categories 10, 11, 12, 13, 14, 15, 16, 17, 18, and 19 have 8 samples each. Categories 10, 11, 12, 13, 14, 15, 16, 17, 18, and 19 have 9 samples each. Categories 10, 11, 12, 13, 14, 15, 16, 17, 18, and 19 have 10 samples each. Categories 10, 11, 12, 13, 14, 15, 16, 17, 18, and 19 have 11 samples each. Categories 10, 11, 12, 13, 14, 15, 16, 17, 18, and 19 have 12 samples each. Categories 10, 11, 12, 13, 14, 15, 16, 17, 18, and 19 have 13 samples each. Categories 10, 11, 12, 13, 14, 15, 16, 17, 18, and 19 have 14 samples each. Categories 10, 11, 12, 13, 14, 15, 16, 17, 18, and 19 have 15 samples each. Categories 10, 11, 12, 13, 14, 15, 16, 17, 18, and 19 have 16 samples each. Categories 10, 11, 12, 13, 14, 15, 16, 17, 18, and 19 have 17 samples each. Categories 10, 11, 12, 13, 14, 15, 16, 17, 18, and 19 have 18 samples each. Categories 10, 11, 12, 13, 14, 15, 16, 17, 18, and 19 have 19 samples each. Categories 10, 11, 12, 13, 14, 15, 16, 17, 18, and 19 have 20 samples each.

A horizontal bar chart consisting of 20 black bars of varying lengths, arranged in two groups of 10. The bars are positioned on a white background with small gaps between them. The top group of bars is generally longer than the bottom group.

A large number of black horizontal bars of varying lengths, likely representing data points or categories in a visualization. The bars are arranged in a grid-like pattern, with some bars being significantly longer than others, indicating a wide range of values or frequencies. The lengths of the bars correspond to the data values, with the longest bars at the top and the shortest at the bottom. The bars are solid black and have no internal structure, representing a single data series or category.

A large number of black horizontal bars of varying lengths, likely representing data points or categories in a visualization. The bars are arranged in a grid-like pattern, with some bars having small white dashes at their left ends. The lengths of the bars vary significantly, with many being relatively short and a few being very long, creating a visual representation of data distribution or frequency.

A series of horizontal black bars of varying lengths, likely representing data points or bars in a chart. The bars are arranged in a grid-like pattern, with some bars being significantly longer than others, indicating a range of values or frequencies. The lengths of the bars correspond to the data points in the following table:

A horizontal bar chart consisting of 20 black bars of varying lengths. The bars are arranged in two main groups: a top group of 10 bars and a bottom group of 10 bars. The bars in the top group are generally longer than those in the bottom group. The bars are separated by small gaps.

A large number of black horizontal bars of varying lengths, likely representing data in a redacted table. The bars are arranged in a grid-like pattern, with some rows having more bars than others. The lengths of the bars vary significantly, with some being very short and others being very long. The overall effect is a dense, abstract pattern of black lines on a white background.

A large number of black horizontal bars of varying lengths, likely representing data points or categories in a visualization. The bars are arranged in a grid-like pattern, with some bars being significantly longer than others, indicating a range of values or frequencies. The lengths of the bars correspond to the data points listed in the table below.

A large grid of black horizontal bars on a white background, representing a redacted document. The bars are arranged in a grid pattern, with some bars being longer than others, creating a visual representation of a document that has been heavily redacted or obscured.

Term	Percentage
GMOs	~10%
Organic	~75%
Natural	~70%
Artificial	~15%
Organic	~75%
Natural	~70%
Artificial	~15%
Organic	~75%
Natural	~70%
Artificial	~15%
Organic	~75%
Natural	~70%
Artificial	~15%

8.3.1.2.13. Daily (Mobile Phone-Based) Assessments

Daily assessments will be derived for Baseline, Day 14, and Day 42 using the mean of non-missing assessments for 7 days as described in the [Table 2](#) below. The baseline measurement will be calculated as the mean of days immediately preceding to first dose day. The precision level of averages is to keep one decimal place. [Table 2](#) lists visit deviation. If there are missing assessments for more than 4 days among 7 days, the derived mean will be considered as missing.

Table 2. Analysis Visit Derivation for Daily Mobile Assessments

Scheduled Visit	Derivation for averaging
Baseline *	> Day -7 and \leq Day 1
Day 14	> Day 7 and \leq Day 14
Day 42	> Day 35 and \leq Day 42

* Day 1 assessment will be collected prior to the first dosing per protocol. For PVT and DSST, if Day 1 assessment is collected after the first dose or not available, available non-missing assessments for 7 days prior to the first dose will be used (i.e., > Day -8 and \leq Day -1).

8.3.1.2.13.1. Psychomotor Vigilance Task

The PVT has participants press a button in response to a simple visual stimulus provided at random intervals. The primary measure is the number of missed responses, which describes the participant's sustained attention. This test will be administered each morning during the Treatment Period using a mobile device. At scheduled clinic visits, the task will be performed in the clinic under observation by study staff, otherwise the participant will perform this task remotely (at home).

The key outcome measures are:

- PVT Total False Positives
- PVT Total Timeouts
- PVT Slope of Linear Fit
- PVT Reaction Latency (mean)
- PVT Reaction Latency (Coefficient of Variation)
- PVT Total Hits

Other outcome measures are:

- PVT Reaction latency (variance)
- PVT Mean Press Length

8.3.1.2.13.2. Digit Symbol Substitution Test

The DSST is widely used to monitor changes in cognitive function over time and for early detection of cognitive dysfunction. The task requires participants to use a reference key to pair specific numbers with geometric figures. The number of correct pairings achieved within 90 seconds is summed to generate a total score. This test will be administered each morning during the Treatment Period using a touch screen mobile device. At scheduled clinic visits, the task will be performed in the clinic under observation by study staff, otherwise the participant will perform this task remotely (at home).

The key outcome measures are:

- DST Total Correct
- DST Total Incorrect
- DST Correct Movement Latency Mean
- DST Incorrect Movement Latency Mean
- DST Correct Response Latency Mean
- DST Incorrect Response Latency Mean

Other outcome measures are:

- DST Correct Movement Latency SD
- DST Incorrect Movement Latency SD
- DST Correct Response Latency SD
- DST Incorrect Response Latency SD

8.3.1.2.13.3. National Sleep Foundation Sleep Diary

Once daily in the morning, participants will briefly answer 5 questions about sleep length, sleep latency, night awakenings, and sleep quality. These questions have been modified from version 6 of the National Sleep Foundation Sleep Diary. This diary will be completed each morning during the Treatment Period using a mobile device. At scheduled clinic visits, the task will be performed in the clinic under observation by study staff, otherwise the participant will perform this task remotely (at home).

Outcome measures are individual items for sleep length, sleep latency, night awakenings, and sleep quality. Sleep length (minutes) is computed as participant get out of bed this morning – time participant went to bed last night. There is no key outcome measure.

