8. STATISTICAL ANALYSIS

8.1. General Considerations

Continuous data will be summarized in terms of the number of participants, mean, standard deviation (SD), minimum value (min), maximum value (max), median, 25th percentile (Q1), and 75th percentile (Q3). The minimum and maximum will be reported with the same number of decimal places as the source (raw) data. Mean, median, Q1, and Q3 will be reported to 1 decimal place more than the source (raw) data. SD and standard error (SE), if applicable, will be reported to 2 decimal places more than the source (raw) data. Least Square Means (LSM) will be reported to 1 decimal place more than the source (raw) data. Confidence intervals (CI) will be presented to one more decimal place than the associated parameter estimate. In general, the maximum number of decimal places reported shall be four for any summary statistic.

Any values that require transformation to standard units (metric or SI) will be converted with the appropriate corresponding precision.

Categorical data will be summarized in terms of the number of participants providing data at the relevant time point (n), frequency counts, and percentages. Percentages will be presented to 1 decimal place unless otherwise specified. Any planned collapsing of categories will be detailed in the SAP text and the data displays.

Percentages will not be presented for zero counts. Percentages will be calculated using the number of participants (n) as the denominator. A missing category shall be included only for categorical variables where no data is available. The missing category will be omitted if there are no missing values for that variable.

All participant data, including those that are derived, that support the tables and figures will be presented in the participant data listings. Some data may be presented only in participant data listing, some may be presented with a corresponding table or figure; these will be indicated in relevant sections below. All summaries will be provided by treatment – either by randomized treatment or actual treatment received.

If a participant takes any dose of SAGE-718, the participant's actual treatment is considered as SAGE-718, regardless of the treatment to which the participant has been randomized.

P-values will be reported to four decimal places, with p-values less than 0.0001 reported as "<0.0001". P-values larger than 0.9999 will be reported as ">0.9999".

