8.3.4.14. Daily (Mobile Phone-Based) Assessments

For PVT and DSST, invalid data will be flagged after science team review by the vendor and will not be used for the analysis.

For key outcome measures specified in [Section 8.3.1.2.13](#), the change from baseline to Day 14 and Day 42 will be summarized using descriptive statistics and analyzed using a similar MMRM model described in [Section 8.3.3.1](#). A plot showing the LSM \pm SE bar over time within each treatment group will also be provided.

Other outcome measures specified in [Section 8.3.1.2.13](#) will be summarized by visit using descriptive statistics.

By-participant listing by visit will be provided.

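### Keeping 7-day mobile averages to one decimal can cost precision or distort estimates for PVT slope and reaction-latency CV, if these vary by only a few hundredths

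*SAP*

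**What the plan says.** SAP Section 8.3.1.2.13 reduces each daily mobile outcome to one value per visit: "Daily assessments will be derived for Baseline, Day 14, and Day 42 using the mean of non-missing assessments for 7 days". Between this averaging rule and the rule for missing days, the same paragraph states: "The precision level of averages is to keep one decimal place". No outcome is exempt. The key PVT outcomes in that section include "PVT Slope of Linear Fit" and the CV of reaction latency. Neither document gives a unit, mean or SD for these two, or says whether the CV is a fraction or a percent.

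Under SAP Section 8.3.4.14, change from baseline to Day 14 and Day 42 in the key outcomes is "summarized using descriptive statistics and analyzed using a similar MMRM model described in" Section 8.3.3.1. That model adjusts for the baseline value.

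Display precision is set elsewhere, in SAP Section 8.1, and relative to the data as recorded: "Mean, median, Q1, and Q3 will be reported to 1 decimal place more than the source (raw) data". The cap there is four decimals.

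**The concern.** A fixed step of 0.1 is trivial for a count but not for a quantity that varies by hundredths. If the rounded mean is the analysed value, the error enters twice, at baseline and at follow-up, before the change is taken. The estimate for such an outcome may then be noisier than the data warrant. When the spread is small against the step, the estimate may also be pulled toward zero or away from it, depending on where values lie relative to a rounding boundary. Display is already governed by Section 8.1, so the rule brings the analysis no benefit. At stake is the interpretation of two supplementary outcomes.

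**Working it through.** **The plan's own figure.** The documents give no figure for rounding. The only benchmark is SAP Section 5.2: effect size 0.75 (0.8/1.07 = 0.748), 30 evaluable per arm, two-sided 0.05, 80% power. A two-sample t-test with 58 df and noncentrality 0.75 × √15 = 2.90 gives 81.5%, so the benchmark reproduces. It is used below only to set the size of a simulated comparison.

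**Inputs.** From the SAP: step h = 0.1, rounding at both visits, baseline as covariate. Assumed, because the documents do not say: normal 7-day means, their SD and centre, and the correlation ρ between baseline and follow-up.

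**Step 1: rounding error.** The maximum is 0.05. The SD is 0.1/√12 = 0.029 and the variance 0.000833.

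**Step 2: approximate loss when the SD is not small against the step.** With k = 0.000833/SD², the baseline-adjusted residual variance is multiplied by about [(1 + k) − ρ²/(1 + k)]/(1 − ρ²). At ρ = 0.7:
- Fractional CV, SD 0.05: k = 0.333, and (1.333 − 0.3675)/0.51 = 1.89. Simulation gives 1.84, so the SE is multiplied by √1.84 = 1.36.
- SD 0.2: k = 0.0208, and (1.0208 − 0.4800)/0.51 = 1.06, an SE increase of about 3%.
- CV in percent, SD 5: k = 0.000033, ratio 1.0001.

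**Step 3: small SD, by simulation.** With only a few rounding cells in use, the formula in step 2 fails. For a slope with mean 0 and SD 0.03, the residual variance is multiplied by 1.76 at ρ = 0.7 (SE × √1.76 = 1.33) and by 1.33 at ρ = 0.5 (SE × √1.33 = 1.15).

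**Step 4: distortion at SD 0.02.** Take ρ = 0.7 and a true effect of 0.75 SD of change. The effect is 0.75 × √(2 × 0.3) = 0.581 SD, or 0.0116.
- Centre 0.25, on a boundary: the rounded means differ by 0.1 × [Φ(0.581) − 0.5] = 0.1 × 0.219 = 0.0219. The ratio to the truth is 0.0219/0.0116 = 1.9.
- Centre 0.20, boundaries 2.5 SD away: before the effect, rounding up and down cancel. After it, the shift is 0.1 × [P(Z > 1.919) − P(Z < −3.081)] = 0.1 × (0.0275 − 0.0010) = 0.0027. The ratio is 0.0027/0.0116 = 0.23.

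**Step 5: effect on power.** Simulation with 30 per arm, ANCOVA on change with baseline as covariate, ρ = 0.6, effect 0.75 SD of change, 800 runs per cell:

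| SD of 7-day mean | Centre | Power unrounded | Power rounded | Estimate / truth |
|---|---|---|---|---|
| 0.01 | 0 or 0.20 | 0.88 | 0.00 | 0.00 |
| 0.02 | 0 or 0.20 | 0.89 | 0.02 | 0.23 |
| 0.02 | 0.25 | 0.87 | 0.55 | 1.78 |
| 0.03 | 0 to 0.25 | 0.87–0.90 | 0.38–0.60 | 0.73–1.27 |
| 0.05 | 0 to 0.25 | 0.87–0.90 | 0.68–0.72 | 1.00–1.02 |
| 0.1 | 0 to 0.25 | 0.87–0.88 | 0.80–0.84 | 0.98–1.01 |
| 0.2 | 0 to 0.25 | 0.87–0.92 | 0.87–0.90 | 1.00–1.02 |

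At SD 0.2 the largest loss in any cell is 0.886 − 0.868 = 1.8 points. At SD 1.0 it is 0.3 points or less.

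**The case against.** The strongest reply is that the harm depends on scales the documents do not give. If the CV is a percent, or the slope has an SD of 0.2 or more, almost nothing is lost. That stands, and it makes the point conditional.

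Second, the sentence does not say that the MMRM uses the rounded value. That also stands. The reading rests on the sentence's place in the derivation rather than among the display rules, and on its conflict with Section 8.1 if it were a display rule for outcomes recorded to one or more decimals.

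Third, the reach is narrow. Of the 12 key PVT and DSST measures, five are counts and five are latency means, which are unaffected if in milliseconds (a unit the SAP also leaves open). That leaves slope and CV. SAP Section 6.1 notes that the protocol set no analysis objective for the mobile assessments.

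A reader might infer that rounding erases most of the signal in slope and CV, so that a null result on them would be an artefact. The documents do not support this. It needs an SD of about 0.02 or less, which they do not state. At an SD of 0.05 the estimate is essentially unbiased and most of the power remains, and near a boundary the effect is inflated rather than erased.

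A reader might also cite the unadjusted change score, whose variance roughly doubles (×2.04 for CV, ×2.17 for slope) with 70% and 88% of changes exactly zero. The planned model adjusts for baseline, so the relevant factors are 1.84 and 1.76, and the share of zero changes does not measure lost power.

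None of these replies gives a reason to keep the rule.

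**Conclusion.** The point holds in conditional form. The SAP places a fixed one-decimal rule in the derivation of values that go into an MMRM, without units for the two key outcomes most exposed to it. If PVT slope or CV varies between participants by a few hundredths, the SE rises by about a third at ρ = 0.7 (15% for slope at ρ = 0.5). For a slope with SD 0.03, the estimate can also fall to about 0.73 of the truth or rise to about 1.27, depending on the centre. At still smaller spreads the estimate is unreliable in either direction. On larger scales nothing of consequence is lost. All of this assumes normal 7-day means and the stated SDs, centres and correlations, none of which comes from the documents. WAIS-IV Coding, its sample size and its power are untouched.

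**What to change.** In SAP Section 8.3.1.2.13, replace the one-decimal sentence with:

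> Averages are carried at full precision for all derivations and models; rounding is applied only for display, per Section 8.1.

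If display was all that was meant, this makes it explicit; if not, it removes the loss. In the simulation, power on unrounded averages is about 0.87 to 0.92 at every scale. The cost is one sentence before database lock, with no added participants, visits or data and no analytical downside.
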